## **Quantitative Data Analysis**

See Statistical Procedures Attachment.

## **Qualitative Data Analysis**

We will conduct semi-structured individual interviews using an iterative interview guide (see attached interview guide) developed following the recommendations of Kallio 2016 which includes 1) internal testing by the research team; 2) expert assessment by specialists outside the research team; and 3)

field-testing with the potential study participants. The guide includes open-ended questions and probes designed to generate an explanatory model of participants' experience living with HIV and communicating about it in a clinical setting. Recruitment for in-depth interviews will continue until we have reached data saturation, when no new information is gleaned from the most recent interviews. Analysis of transcripts from in-depth interviews (Aim 4) will be guided by a qualitative descriptive (QD) methodology and will include conventional QD content analysis methods such as inductive line-by-line latent coding. Recognizing that the researcher is the instrument in QD methods, only one researcher will conduct all interviews. An iterative content analysis method will then be used to generate codes and extract meaning from each question. A coding guide will be developed by one member of the research team after initial review of a subset of transcripts. Other team members will then review and refine the coding guide. Then, two members of the research team will code each transcript and discrepancies will be resolved by discussion until consensus is achieved. Analyses will be conducted in Spanish then translated to English for final dissemination. NVivo will be used to support data management and Gioia's methodology to ensure rigor in qualitative research will be followed. A summary of the findings will be shared with a subset of participants (selected through purposive sampling) to determine if the findings resonate with them ("member check"). Any changes suggested will be made and the findings will be finalized.

## **Privacy and Data Security**

All data collected will be coded to ensure confidentiality. Data from baseline and follow up assessments will be collected in Columbia University's REDCap online survey management system then downloaded and stored on Columbia University Servers. Audio recordings of intervention visits and in-depth interviews will also be coded then saved on Columbia University Servers. Only members of the research team will have access to the list that matches codes with participants. That list will be stored in password protected Columbia University Servers.

Data will be collected in a private interview setting to maintain participant comfort and confidentiality. All collected data will be coded. Only the study team will have access to the file which can link participants to their study data. It will be password protected on Columbia University Servers.

Audio Recordings will be transcribed by a secure transcription service outside of Columbia after a data use agreement has been signed.

## **Procedures**

Columbia University researcher, [name], will be in charge of completing and overseeing all study procedures in collaboration with local study team members.

### **Study Setting**

All study activities will take place at Clínica de Familia La Romana, which is a non-profit health center in the Dominican Republic licensed by the Dominican Ministry of Health that specializes in the education, diagnosis, treatment, and management of sexually transmitted infections, including HIV. More than 40 interdisciplinary professionals offer free care, treatment, and support to over 2,000 persons living with HIV during more than 17,000 visits annually.

### **Intervention**

Interventionists (N=2), will be physicians with two or more years of experience providing care to adults living with HIV at the Clinic. They will initially attend a training to guide patient education with infographics in a clinical setting, and will receive coaching on intervention fidelity, including how to maintain it. During the intervention, in normal clinic visits, interventionists will guide education using the paper-based set of infographics developed in preliminary studies. Infographics will provide a visual representation of the pertinent information to be included. Paper versions of the infographics to

be used during the intervention will be kept in participants' medical records to enable easy access during visits, prevent providers from accessing them with non-study participants, and enable providers to mark graphics while teaching. Intervention fidelity will be verified by audio recording one-half of total intervention visits with equal numbers of visits over the three time points and an equal number of recorded visits with each interventionist with patient permission as is detailed in the informed consent document. Members of the study team will listen to audio recordings to confirm interventionists are using infographics during visits as specified in the intervention training, that both providers are using them in the same way, and that they are delivering the intervention consistently across visits.

Additionally, participants will be asked about provider's infographic use during follow up assessments.

Participant eligibility will be verified in the medical records of patient's scheduled appointments at the beginning of each day. Eligible participants will then be recruited by the receptionist when they present to the Clinic for their regular clinic visit and referred to speak to an on-site researcher who will further introduce the study (see attached recruitment script) and then if a participant is interested, complete the informed consent process. After completing the informed consent process, participants will complete a baseline assessment using REDCap software with the help of a study team member prior to their visit (Table 1). Participants will then receive the intervention during the enrollment visit and at three and six-month visits and complete the follow up assessment at each of these time. Time intervals were selected as CD4 count and viral load may change as early as three months after ART initiation. Interventionists will time visits and no extra time will be allowed for study visits. Following their six-month study visit, participants will be asked to participate in in-depth interviews. At the nine-month study visit, participants will complete a follow up assessment to assess ability to recall information from infographics over time. At the end of the study, the interventionists will be interviewed to assess feasibility of infographic use in a clinical setting.

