**The purpose of this study is, therefore, to complete the following research aims:**

**Aim 1.** Explore the usability of infographics (designed during preliminary studies) to facilitate HIV-related clinician-patient communication and to assess their feasibility using established guidelines.

**Aim 2.** Pilot test measures to assess treatment outcomes within this population and estimate measurement parameters for future efficacy testing (means and standard deviations).

**Aim 3.** Measure the effect of infographic use on PLWH's treatment outcomes at three-, six- and nine-month intervals following initial exposure to the intervention.

**Aim 4.** Generate an explanatory model of HIV infection among patients in this clinical context and explore how it may be used to guide HIV-related communication using infographics.

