## **Study Design**

To complete the study aims, a mixed methods study that includes a single group pretest posttest study design will be used to pilot test the infographic intervention. In-depth interviews will be completed with a selection of participants to explore participant perceptions of HIV-related communication using infographics. Data will be collected from participants through baseline (at enrollment) and follow up assessments (at 3-, 6-, and 9-month follow up visits). Follow up interviews will be conducted with the providers involved in the intervention to ascertain their perspectives on the clinical utility of infographics. Participant's most recent CD4 count and viral loads will be collected from participants' medical records at each study visit.

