## Measures

Outcome selection was guided by a conceptual model to theoretically guide communication studies. This model illustrates pathways through which clinician-patient communication may influence health outcomes in the short (proximal), medium (intermediate), and long-term. Primary outcomes of CD4 count and viral load will be collected from patient medical records at each study visit. Measures of information recall/comprehension, engagement with clinician, satisfaction with care, self-efficacy to manage HIV, adherence, health related quality of life, and health status (self-reported status and CD4 count and viral load) will all be included in the baseline and follow up assessments.

**Baseline assessments** will collect demographic information, evaluate health literacy level, and contain the instruments to assess outcome measures.

**Follow up assessments for PLWH** will include the outcome measures as well as open-ended questions exploring the usability of infographics, satisfaction with designs and recommendations for improvement. Open-ended questions regarding interventionists' communication strategies and intervention delivery will be included to assess providers' communication variability. Participants' responses to open-ended questions on the follow up assessments will be audio-recorded with participants' permission and then transcribed to enable more effective analysis.

**Follow up interview for health care providers.** Interventionists will complete a semi-structured interview containing questions on the following aspects of feasibility: acceptability, demand, implementation, practicality, adaptation, integration, expansion, and limited-efficacy testing and

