**Table 1. Research activity at each time point**

Time point	Activity
Enrollment	
 
• Health literacy assessment
 
• Baseline assessment
 
• Exposure to intervention
 

3 months	
 
• Exposure to intervention
 
• Follow-up assessment
 

6 months	
 
• Exposure to intervention
 
• Follow-up assessment
 

9 months	
 
• Follow up assessment
 

Study end	
 
• Follow-up interview for health care providers
 

Note: In-depth interviews will take place after participant's 6 month visits

questions elucidating feedback on infographic design and suggestions regarding their effective incorporation into clinical visits.

**In-depth interviews with PLWH.** To describe PLWH's perceptions of HIV-related communication in a clinical setting and how it may be influenced by infographic use, directed content analysis guided by McGuire's Classic Input-Output Framework for Constructing Persuasive Messages will be used. In-depth interviews will be conducted using a semi-structured interview guide in a private setting by a study team member and will be audio-recorded and transcribed.

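### Does the unstated order of infographic exposure and assessment at 3 and 6 months undermine the HIV-related knowledge contrasts?

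*Protocol*

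**What the plan says.** At enrollment the order is explicit. The Protocol's Intervention section says that "participants will complete a baseline assessment using REDCap software with the help of a study team member prior to their visit", and the intervention follows. For the later visits the same section says that they will "receive the intervention during the enrollment visit and at three and six-month visits and complete the follow up assessment at each of these time". The two activities are joined by a plain conjunction, with no before or after. In Table 1 the 3- and 6-month rows list "Exposure to intervention" and then the follow-up assessment. The 9-month row has an assessment only, and the text gives that visit its own purpose: "participants will complete a follow up assessment to assess ability to recall information from infographics over time".

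Aim 3 looks at outcomes at "three-, six- and nine-month intervals following initial exposure to the intervention". Under Measures, the follow-up assessment "will include the outcome measures as well as open-ended questions exploring the usability of infographics". The primary outcomes are handled separately: "Primary outcomes of CD4 count and viral load will be collected from patient medical records at each study visit".

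The design is a "single group pretest posttest study design". The SAP models HIV-related knowledge by GEE, with visit and new-patient status as the only independent variables, and estimates the change from baseline at 3, 6 and 9 months. It mentions neither the order within a visit nor the time since the latest exposure.

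**The concern.** The protocol fixes the order at one visit and leaves it open at the two visits where it affects what a knowledge score means. A score taken minutes after the clinician has gone through the infographics reflects partly what was just shown. A score taken before that conversation reflects what was kept since the last visit. If exposure came first at 3 and 6 months, those two contrasts mix retained gain with same-day recall, and the 9-month contrast does not. A fall in knowledge from 6 to 9 months could then be true decay or simply the loss of same-day recall. With no control group, the data could not separate the two. Knowledge is one of six outcomes chosen for formal analysis, and Aim 2 wants means and standard deviations for planning a later trial, so the meaning of the score has some practical weight.

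**Working it through.** **The plan's own figure.** The SAP aims for 35 to 40 participants and allows 20% attrition: 40 / (1 − 0.20) = 50, which matches the 50 recruited. The present point does not depend on this number.

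**Schedule inputs** (Protocol, Intervention and Table 1): exposures at months 0, 3 and 6; follow-up assessments at months 3, 6 and 9.

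**Formula.** For an assessment at month t, the lag is t minus the month of the latest exposure already received, and the count is the number of exposures received by then. If exposure comes first, an exposure in month t counts. If assessment comes first, it does not.

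| Assessment | Exposure first: lag; count | Assessment first: lag; count |
|---|---|---|
| 3 months | 3 − 3 = 0; 2 | 3 − 0 = 3; 1 |
| 6 months | 6 − 6 = 0; 3 | 6 − 3 = 3; 2 |
| 9 months | 9 − 6 = 3; 3 | 9 − 6 = 3; 3 |

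Three things follow.

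1. The difference in kind is real under one order only. Exposure first gives lags of 0, 0 and 3 months. Assessment first gives 3, 3 and 3.
2. Neither order makes the three contrasts alike. With assessment first they still follow 1, 2 and 3 exposures, so re-ordering would equalise the lag but not the amount of teaching received.
3. The 9-month contrast is the same under both orders: three exposures, about 3 months after the last.

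**Which order is more likely.** Table 1's enrollment row runs baseline assessment, then exposure, which agrees with the stated sequence. The 3- and 6-month rows put exposure first. The follow-up assessment also asks about usability, delivery and the provider's use of the infographics, which fits administration after the visit. Exposure first is the more natural reading, but it is an inference.

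**What the SAP estimates.** Its target is the change in score from baseline to each visit. Same-day recall is part of the score at that visit, so it does not bias that quantity. It would be a bias only for a different target, the change retained since the previous visit, which the SAP does not name.

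**Size.** The documents give no knowledge scores, no standard deviations and no same-day effect. Any error rate for a confidence interval would come from an assumed bias set against a target the SAP does not use, so none is given here.

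**The case for a change.** The best case for acting is that the remedy looks cheap: complete the instruments before the clinician visit, as at baseline, and keep the usability questions after it. All knowledge scores would then be taken about 3 months after the latest exposure, and Aim 2's means would carry over to a later trial that assesses before the visit.

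Part of this stands. The order is not written down in the available text, and a reader of the results will want to know it.

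The remedy is less clean than it looks. Knowledge just after a teaching visit is a legitimate proximal outcome in the conceptual model described under Measures. The assessment also covers engagement with the clinician and satisfaction with care. Asked before the visit, those questions would refer to a study visit about three months earlier. The follow-up form would have to be split in two. The SAP is written in the past tense, which suggests the visits are complete, so a new visit order would probably come too late.

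A milder request, one sentence in the SAP on the order used, is reasonable. It supplies a missing detail and corrects no estimate, and anyone reporting the trial can supply it from how the visits were run.

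**Conclusion.** No change to the plan is needed. There is a gap in the description: the order within the 3- and 6-month visits is not stated. Its possible effect is confined to the interpretation of secondary, self-reported outcomes, chiefly HIV-related knowledge at two of three follow-up visits. If exposure came first, those two scores have a lag of 0 months, against about 3 months at the 9-month visit. If assessment came first, all three lags are about 3 months and the point disappears.

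For the effect to exist, three assumptions must hold that the documents do not settle: that the listed order was followed, that the knowledge items overlap the infographic content, and that same-day teaching raises the score. A fourth is needed to link the 9-month recall purpose to the analysis: that the SAP's knowledge variable is the protocol's recall and comprehension measure.

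The SAP's contrasts are valid for what they set out to estimate. The primary outcomes, CD4 count and viral load, do not depend on when the questionnaire was given. The protocol already sets aside an exposure-free visit for recall over time. The sensible reading is to report the order used, to describe the 3- and 6-month knowledge changes as including same-day recall if exposure came first or the order varied, and to rest any statement about retention on the 9-month contrast. That contrast can show retention after three exposures but not after one.

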## Measures

Outcome selection was guided by a conceptual model to theoretically guide communication studies. This model illustrates pathways through which clinician-patient communication may influence health outcomes in the short (proximal), medium (intermediate), and long-term. Primary outcomes of CD4 count and viral load will be collected from patient medical records at each study visit. Measures of information recall/comprehension, engagement with clinician, satisfaction with care, self-efficacy to manage HIV, adherence, health related quality of life, and health status (self-reported status and CD4 count and viral load) will all be included in the baseline and follow up assessments.

**Baseline assessments** will collect demographic information, evaluate health literacy level, and contain the instruments to assess outcome measures.

**Follow up assessments for PLWH** will include the outcome measures as well as open-ended questions exploring the usability of infographics, satisfaction with designs and recommendations for improvement. Open-ended questions regarding interventionists' communication strategies and intervention delivery will be included to assess providers' communication variability. Participants' responses to open-ended questions on the follow up assessments will be audio-recorded with participants' permission and then transcribed to enable more effective analysis.

**Follow up interview for health care providers.** Interventionists will complete a semi-structured interview containing questions on the following aspects of feasibility: acceptability, demand, implementation, practicality, adaptation, integration, expansion, and limited-efficacy testing and

**Table 1. Research activity at each time point**

Time point	Activity
Enrollment	
 
• Health literacy assessment
 
• Baseline assessment
 
• Exposure to intervention
 

3 months	
 
• Exposure to intervention
 
• Follow-up assessment
 

6 months	
 
• Exposure to intervention
 
• Follow-up assessment
 

9 months	
 
• Follow up assessment
 

Study end	
 
• Follow-up interview for health care providers
 

Note: In-depth interviews will take place after participant's 6 month visits

questions elucidating feedback on infographic design and suggestions regarding their effective incorporation into clinical visits.

**In-depth interviews with PLWH.** To describe PLWH's perceptions of HIV-related communication in a clinical setting and how it may be influenced by infographic use, directed content analysis guided by McGuire's Classic Input-Output Framework for Constructing Persuasive Messages will be used. In-depth interviews will be conducted using a semi-structured interview guide in a private setting by a study team member and will be audio-recorded and transcribed.

## Recruitment and Consent

Describe how participants will be recruited

At the beginning of each recruitment day, participant's eligibility will be verified in the medical records of patients who have appointments scheduled for that day. The receptionists will then refer eligible participants to speak with an on-site researcher when they present to the Clinic for their regular clinic visit. The on-site researcher will further introduce the study using the recruitment script, answer any questions the person has, and continue with informed consent if the individual indicates interest in study participation.

Describe how participants' written consent will be obtained

Informed consent will be completed by an on-site study team member in a private space. The complete informed consent form will be read to participants, comprehension of procedures will be verified by short questions in the consent forms, and participants will be encouraged to ask questions prior to signing the form. A signed copy of the informed consent form will be stored in a locked file cabinet in a locked office in the Clinic. Participants will be given a copy of the informed consent form for their records.

## Research Aims and Abstracts

Research Question(s)

**Research Question 1:** To what extent are the infographics designed during preliminary studies a feasible and useful method to facilitate HIV-related clinician-patient communication?

**Research Question 2:** How efficacious are these measures (described in the procedures section) to assess treatment outcomes among this population and what are their measurement parameters (means and standard deviations) in this population?

**Research Question 3:** How much does infographic use during clinic visits influence PLWH's treatment outcomes at three-, six- and nine-month intervals following initial exposure to the intervention?

**Research Question 4:** What are PLWH's perceptions of HIV-related communication including infographic use during a clinical visit with a healthcare provider?

Scientific Abstract

The Caribbean has among the highest HIV prevalence in the world. Regionally, the majority of HIV/AIDS cases are located on the island of Hispaniola, comprised of the Dominican Republic (DR) and Haiti. Due to a large international response and widespread availability of antiretroviral therapy (ART), in recent years the incidence of HIV in the DR has declined and prevalence hovers around 1% in the general population. The effective and long-term management of this complex chronic condition depends on infected individuals being able to acquire ART and apply the learned information and self-management skills that lead to optimal adherence. Unfortunately, in developing countries, such as the

DR, various disparities (economic, educational, social) may make it more difficult for individuals to acquire and understand the health information needed for effective self-management. Health care providers in these settings can help patients understand pertinent health information by offering it in targeted, culturally-, and literacy-appropriate ways, such as by using visual representations of information e.g. infographics. Participatory design of infographics supports presentation of information in a culturally appropriate and visually appealing format which can improve information understanding, health behaviors, attention span, and ability to recall information. In preliminary studies, a set of infographics was developed using a participatory design method. This next study phase is to rigorously assess if using these infographics is a feasible, acceptable, and efficacious method to enhance HIV-related clinician-patient communication and lead to improved patient outcomes. Additionally, an understanding of the cultural factors that may influence clinician-patient communication using infographics in a clinical setting will provide valuable information regarding how to improve clinical communication with this population.

